The intervention group for this study are those who will utilize the smartphone app to complete the home-based portion of physical therapy following TKA. The control group are those who have completed traditional home health physical therapy following TKA. Inclusion criteria for the study consists of participants aged 45 to 64, the participant will have undergone unilateral TKA, and the participant should be discharged directly to home from the hospital. Participant's data from the intervention group will be excluded from the study if they do not engage with the app within 24 hours of discharge from the hospital, if the participant neglects to engage with the app over any 24-hour period during the study, or if the participant is readmitted to the hospital at any point during the home bound portion of their recovery.

Subjective outcomes for the participants in the intervention group will be assessed by the Short MAC and objective outcomes will be assessed by measuring total knee ROM improvement. The intervention participants' self-reported frequency of app usage will be compared to the participants' outcomes to determine the dose-response of the app. The Short MAC has been previously shown to be a reliable, valid, and responsive indicator of qualitative improvement in a patient's functional status post-TKA and total hip arthroplasty (THA) by Whitehouse et al (1). Minimum important change for Short MAC has been found to be 7.9 points for small change, 8.4 points for medium change, and 12.1 points for large change (2). The total knee ROM

improvement in the treatment group will be compared against a control group of patients who have completed traditional home care from a variety of physical therapists following TKA.

The primary hypothesis is that the intervention group will show a statistically equal outcome to the control group, demonstrating the efficacy of a low-cost alternative to traditional home care. The null hypothesis is that the research group will not show a statistically equal outcome to the control group. The first alternative hypothesis is that the intervention group will show a statistically significant improvement over the control group. The second alternative hypothesis is that the control group will show a statistically significant improvement over the intervention group.

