Data for the control group will be taken from approximately 30 individuals aged 45 to 64 that have previously completed traditional home health physical therapy care from a variety of physical therapists following TKA. Data for the intervention group will be taken within 48 hours of being discharged from the hospital from approximately 30 participants who agree to use the smartphone app to complete the home-based physical therapy portion of their recovery from TKA. Intervention group participants will complete an introductory meeting with the physical therapist in-person to onboard the patient to the app and perform the initial data collection. Participants in the intervention group will be encouraged to engage with the app 3 to 5 times per day as able. The intervention participant will have the ability to communicate any questions or concerns to the Physical Therapist via e-mail or phone call throughout the homebound portion of their recovery. For safety monitoring, a physical therapist will contact the intervention group participant via phone or e-mail every 24 to 48 hours to ensure no adverse events have occurred. A final in-person meeting will occur between the Physical Therapist and the participant at the conclusion of the homebound portion of the participants' recovery for the purpose of final data collection. A two-tailed t-test for two independent groups will be used to compare the means for total ROM improvement between the intervention group and the control group. Data from the Short MAC will be used to describe the overall subjective effect of the intervention on the patient's functional abilities. The relationship between the Participants self-reported frequency of app usage and their combined subjective and objective outcomes will be used to understand the dose-response of the app. Information about dose-response will be integral in establishing guidelines regarding frequency of app usage for optimal results.

Conclusion

Traditional home health care for individuals recovering from unilateral TKA is expensive and provides a higher level of service than most individuals, aged 45 to 64, require. Use of smartphone technology has the potential to drive down costs while maintaining outcomes for this patient population. The proposed randomized controlled trial would determine the efficacy and proper dose-response of a smartphone app to reduce costs and maintain outcomes for the desired patient population compared to traditional home care.

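### The aim is to show that the app equals home care, but the only between-group test named is a difference test that cannot show equality

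*Protocol*

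**What the plan says.** All the relevant text is in the Methods section of the protocol.

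- Primary hypothesis: "The primary hypothesis is that the intervention group will show a statistically equal outcome to the control group". The same sentence goes on to treat this result as proof that the app works as a cheaper substitute for home care.
- Null hypothesis: "The null hypothesis is that the research group will not show a statistically equal outcome to the control group".
- Alternatives: one reads "The first alternative hypothesis is that the intervention group will show a statistically significant improvement over the control group"; its mirror image reads "The second alternative hypothesis is that the control group will show a statistically significant improvement over the intervention group".
- Test: "A two-tailed t-test for two independent groups will be used to compare the means for total ROM improvement".
- Size: "Data for the control group will be taken from approximately 30 individuals aged 45 to 64" is the wording for controls; the app arm is described as "approximately 30 participants who agree to use the smartphone app".

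The protocol gives no ROM difference small enough to count as equal, no confidence-interval rule, no alpha, no power and no SD for ROM improvement. The only thresholds in the document (7.9, 8.4 and 12.1 points) belong to the Short MAC. That scale is collected in the intervention group only and cannot serve as a ROM margin.

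**The concern.** The hypotheses and the test point in opposite directions. A t-test can reject equality of means, but it has no outcome that rejects inequality. The protocol's stated null therefore cannot be rejected by the test it names. The two alternatives do not help: app better and home care better are the two halves of that same null, not alternatives to it.

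The practical risk is that failure to find a difference is taken as a finding of no difference. That reading rewards a small or noisy study, because wide confidence intervals produce non-significance. It matters here because the result is meant to support replacing home visits with an app on the grounds that outcomes are maintained. An app with a real ROM deficit could pass on this basis.

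**Working it through.** **1. Which t-test results lead where**

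| Result of the named test | Where the protocol's hypotheses place it |
|---|---|
| Significant, app better | First alternative |
| Significant, home care better | Second alternative |
| Not significant | The only result left for the primary hypothesis |

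The protocol does not write out a rule that p > 0.05 means equal. The rule is inferred from this table.

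**2. Inputs**

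- From the protocol (Methods): about 30 per group; two-tailed t-test for two independent groups.
- Assumed: two-sided alpha 0.05; normal data with equal variances; true differences in SD units, because no SD is given.

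The figure of 30 per group cannot be reproduced, since no design inputs accompany it.

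**3. How often a real deficit gives p > 0.05**

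For a true deficit of d SD, the t statistic is noncentral t with df = n1 + n2 − 2 and noncentrality d / √(1/n1 + 1/n2). With 30 and 30, df = 58 and the critical value is 2.002. For d = 0.5 the noncentrality is 0.5 / √(2/30) = 0.5 / 0.2582 = 1.936, which gives power 0.478 and P(p > 0.05) = 1 − 0.478 = 0.522.

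| True deficit | P(p > 0.05), 30 vs 30 |
|---|---|
| 0.3 SD | 79% |
| 0.5 SD | 52% |
| 0.6 SD | 37% |
| 0.75 SD | 19% |
| 1.0 SD | 3% |

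The smallest difference detectable with 80% power is 0.74 SD.

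**4. Effect of a smaller analysed sample**

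The Methods remove intervention participants for any 24-hour lapse in app use or for readmission. The loss rate is not stated, so these are illustrations at a 0.5 SD deficit:

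- 20 app users vs 30 controls: 60%.
- 15 app users vs 30 controls: 66%.
- 15 vs 15, if both groups came in at half size: 74%.

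**5. What 30 per group can exclude**

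The 95% CI half-width is 2.002 × √(2/30) = 0.517 SD. If the SD of ROM improvement were 10 to 20 degrees (assumed), this is about 5 to 10 degrees either side of the estimate.

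**6. An equivalence test at the same size**

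Two one-sided tests (TOST) at 5% each, true difference zero, simulated with estimated SD:

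| Margin | Power, 30 per group | n per group for 80% power, TOST | n per group for 80% power, non-inferiority |
|---|---|---|---|
| 0.3 SD | about 0% | 191 | 175 |
| 0.4 SD | 2% | 108 | 99 |
| 0.5 SD | 22% | 69 | 63 |
| 0.6 SD | 49% | 48 | 44 |
| 0.75 SD | 78% | 31 | 28 |

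Sample sizes use the normal approximation with margin m in SD units: 2 × ((1.645 + 1.282)/m)² for TOST, and 2 × ((1.960 + 0.842)/m)² for non-inferiority at one-sided 0.025. At m = 0.5 the TOST formula gives 68.5, rounded up to 69. In simulation, 30 per group reaches 81% power at a margin of 0.77 SD. False equivalence when the true difference sits on the margin is about 5% or less.

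**The case against.** The strongest reply is that the protocol never states a success rule. It says only that the t-test will compare the means, and an analysis plan not shown here could add a margin and an interval rule. This is right as far as it goes: the p > 0.05 rule is an inference, and the absent margin would be a weak finding by itself. The contradiction remains, however. The protocol fixes an equality hypothesis, a null of inequality and a difference test. A later plan that kept the test would inherit the error, and one that replaced it would depart from the protocol.

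Three further points limit the claim without removing it.

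- Whether 0.5 SD matters to patients cannot be judged from the document, and at 1 SD the test would miss the deficit only 3% of the time. The problem lies with moderate deficits.
- The app-use and readmission exclusions apply to the intervention group alone, so losses from them would produce an unbalanced comparison. The 60% and 66% figures fit that situation better than 74%.
- The 5% error rate of an equivalence test covers sampling error only. Controls are people who had already completed home care, and non-engaging or readmitted app users are dropped. No choice of test corrects bias from either source.

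**Conclusion.** The concern holds. As written, the named test cannot support the primary hypothesis, and the only route to the claim of efficacy is a non-significant p-value. At the planned size, a true app deficit of 0.5 SD would be compatible with that claim in about half of trials (52%), and a deficit of 0.75 SD in about one in five (19%). These figures assume two-sided alpha 0.05, 30 analysed per group and normal data with equal variances. The conversion to degrees also assumes an SD of 10 to 20 degrees. The mismatch between hypothesis and test depends on none of these assumptions. It affects the primary comparison and must be fixed before data are analysed.

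**What to change.** Make these changes to the Methods before any outcome data are seen:

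1. State a margin in degrees of ROM improvement, justified clinically and not chosen to suit the sample size.
2. Restate the hypotheses. For equivalence, the null is that the groups differ by at least the margin and the alternative is that they differ by less. For non-inferiority, the null is that the app is worse by at least the margin.
3. Replace the t-test decision rule. With the difference taken as app minus home care, conclude equivalence only if the 90% CI lies wholly within plus or minus the margin (TOST at 5%), or non-inferiority only if the lower limit of the two-sided 95% CI lies above minus the margin.
4. State that p > 0.05 alone, or an interval that crosses the margin, is inconclusive.
5. Report the margin that about 30 per group can exclude with useful power: about 0.77 SD for equivalence, or about 0.72 to 0.74 SD for non-inferiority (normal approximation and exact t), each at 80% power.

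Correcting the inference costs protocol wording and the work of justifying a margin; it needs no new measurements and no extra patients. The price is that the trial may honestly end inconclusive, and with a margin near 0.5 SD it probably would (22% power for equivalence). If the justified margin is that narrow, the sponsor can enlarge the trial (69 per group for equivalence or 63 for non-inferiority at 0.5 SD) or keep the present size and present the result as an estimate with its interval, without a claim of equality.

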Traditional Home Health Physical Therapy Versus a Smartphone App for Patients Recovering from Total Knee Arthroplasty During the Home-bound Portion of Recovery: Study Protocol for a Randomized Controlled Trial

by [name] [name], PT, DPT

Study Design

Prospective randomized controlled trial comparing traditional home health care physical therapy to physical therapy provided via a smartphone app for patients recovering from total knee arthroplasty (TKA)

Background

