As of 2013, it was estimated that 4.0 million individuals in the U.S. were living with a TKA, representing 4.2% of the population fifty years of age or older (8). As of 2010, there were 81,489,445 people aged 45 to 64 in the U.S. (4), with a rate of 39.5 total knee arthroplasties per year per 10,000 individuals in that age group (3). Therefore, approximately 322,000 TKAs were performed in 2010 for those aged 45 to 64. A 2010 study from The Centers for Disease Control and Prevention found the average cost of home health care following TKA to be \$3,709 per episode of care per patient (5). This results in nearly \$1.2 billion dollars in U.S. healthcare spending in 2010 for home care following TKA for those aged 45 to 64. The reason for the high cost of home health care may be the state regulations governing home health care agencies. The Louisiana Department of Health and Hospitals states that 'skilled home health care,' found under the definition of 'home health agency' in the official Louisiana Home Health State Regulations, is to include skilled nursing and at least one of the following services: physical therapy, occupational therapy, speech therapy, medical social services, or home health aide services (9). These regulations place pressure, whether conscious or subconscious, on the home health agency to over utilize skilled nursing services for those patients aged 45 to 64 recovering from TKA. Skilled nursing home health care services for this particular patient population usually involves managing the patient's medications and providing wound care services. A cohort study by Bleijenberg et al published in the Journal of the American Geriatric Society in 2017 found that only 10.3% of adults aged 65 to 69, which is above the age cutoff for this prospective study, had difficulty with managing their medications (10). Also, in the author's clinical experience, it is rare for an orthopedic surgeon to allow any other clinician to manage post-operative dressing changes except those clinicians under the surgeon's direct supervision; though further research in this area would be helpful. Furthermore, utilization of TKA, and the home care cost associated with recovery from TKA, is on the rise. As of 2009, the number of primary TKAs performed annually in the U.S. among all age groups exceeded 620,000 procedures, which is more than doubled when compared to the previous decade (7). Smartphones and other technologies may provide a solution to the rising costs of home health care following TKA for those aged

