
45 to 64. Over the past decade, the smartphone has become an integral part of most people's lives. The latest Pew Research Data from February 2018 shows that 73% of individuals aged 50 to 64 own a smartphone (8). Smartphones would allow the patient to have direct multimedia access to a prescriptive exercise program designed by a licensed Physical Therapist without an in-person home visit, as well as to have communication directly with their Physical Therapist through secure in-app messaging or e-mail. The patient would benefit by having reduced intrusion in their home environment, convenient access to their Physical Therapist and their Physical Therapist's plan of care, and financial savings due to the elimination of home health care services following TKA. The Physical Therapist would benefit from the ability to quickly interact with the patient to mitigate any adverse events and to efficiently assist a greater number of patients compared to traditional home-based physical therapy. Third-party payors would benefit from drastically reduced home care costs for those recovering from TKA.

Objectives

The primary objective will be to determine the efficacy of the app for those recovering from TKA compared to traditional home care during the home bound portion of the patient's recovery from TKA by comparing ROM improvement outcomes between the intervention group and the control, as well as measuring the subjective improvement in functional outcomes for the intervention group by using the Short MAC. A secondary objective of the study is to determine the relationship between the intervention participants' self-reported frequency of engagement with the app and their qualitative and quantitative outcomes, otherwise known as the dose-response.

Methods

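### The protocol calls the study a randomized controlled trial that will determine efficacy, but its Methods compare new app users with people whose home care is already finished, so allocation as described cannot be random

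*Protocol*

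**What the plan says.** **Label.** The title reads "Study Protocol for a Randomized Controlled Trial". Study Design reads "Prospective randomized controlled trial comparing traditional home health care physical therapy to physical therapy provided via a smartphone app". The Conclusion again calls the proposed study a randomized controlled trial. The Background, in an aside about age, refers to 10.3% of an older group, "which is above the age cutoff for this prospective study".

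**Claim.** The Objectives state: "The primary objective will be to determine the efficacy of the app for those recovering from TKA compared to traditional home care". In the Methods, the primary hypothesis is that the two groups will have a statistically equal outcome, "demonstrating the efficacy of a low-cost alternative to traditional home care". The Conclusion says the trial would determine efficacy.

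**How the groups are formed (Methods).** "The intervention group for this study are those who will utilize the smartphone app"; "The control group are those who have completed traditional home health physical therapy following TKA". The last paragraph of the Methods adds the source of the controls: "Data for the control group will be taken from approximately 30 individuals aged 45 to 64 that have previously completed traditional home health" physical therapy, from a variety of therapists. The app group is about 30 people who agree to use the app, with data taken within 48 hours of hospital discharge.

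**Analysis (Methods).** A two-tailed t-test for independent groups compares mean improvement in total range of motion (ROM). No significance level is stated.

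**The concern.** Randomisation is what would allow a difference in ROM improvement to be read as an effect of the app. The protocol asserts it three times, but its own account of how people enter each group rules it out.

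Any difference between past home-care patients and current volunteers for an app is then mixed with the app effect. Such differences could lie in calendar time, willingness to use the technology, or how and by whom ROM was measured. The distortion can go either way. It can create a difference where there is none, or hide a real one. The second matters particularly here, because the hoped-for result is equality.

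Reporting the result as randomised evidence of efficacy would be false, whatever the data showed.

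**Working it through.** The protocol has no figure to reproduce: it gives about 30 per group and no alpha, power, SD, effect size or margin. The main check is to set the label against the Methods.

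**1. Label against Methods**

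| Feature | Title, Study Design, Conclusion | Methods |
|---|---|---|
| Allocation | Randomized | No common pool of eligible patients, no ratio and no assignment step |
| Controls | One arm of a prospective trial | People whose home care is already complete |
| App group | The other arm of that trial | People who will use the app, entering by agreeing to it |
| Onboarding, safety contacts, final visit | Not addressed | Written for the app group only |

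**2. Consequence.** Someone whose home care ended beforehand had no chance of being assigned to the app. Someone newly discharged who enters by agreeing to use the app had no chance of being in the previously treated group. Each person's probability of being in a given group is therefore 0 or 1. Random allocation requires a probability strictly between the two. The word *prospective* fits the app group but not the care that the controls received.

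**3. Supporting point: unequal selection.** Taken literally, controls are people who completed home care. App participants' data are removed for not engaging within 24 hours of discharge, for any 24-hour lapse in engagement, or for readmission. These removal rules are stated for the app group only.

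**4. Illustration of what bias does to the t-test.** From the protocol: about 30 per group and a two-sided test. Assumed: alpha 0.05, exactly 30 analysed per group (or 100, for contrast), and a bias of b standard deviations from group formation.

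The test statistic follows a noncentral t distribution with 2n − 2 degrees of freedom and noncentrality b × √(n/2).

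- n = 30: df = 58, √15 = 3.873. For b = 0.5, noncentrality is 0.5 × 3.873 = 1.94.
- n = 100: df = 198, √50 = 7.071. For b = 0.5, noncentrality is 0.5 × 7.071 = 3.54.

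Probability of p < 0.05 when the app truly makes no difference:

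| Bias (SD) | 0 | 0.1 | 0.2 | 0.3 | 0.5 |
|---|---|---|---|---|---|
| n = 30 per group | 0.050 | 0.067 | 0.119 | 0.208 | 0.478 |
| n = 100 per group | 0.050 | 0.108 | 0.291 | 0.560 | 0.940 |

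Simulation with 100,000 trials per cell agrees with every biased cell to within 0.001.

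**5. The same figures for the equality claim.** Suppose the app is truly worse by 0.5 SD and group formation favours it by 0.3 SD (both assumed). The net difference is 0.5 − 0.3 = 0.2 SD. With 30 per group, the chance of a non-significant result rises from 1 − 0.478 = 52% to 1 − 0.119 = 88%.

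**The case against.** **A concurrent reading.** The control wording might mean patients enrolled alongside the app group, whose data are collected once their care ends. The text does not support this. The controls are said to have finished *previously*, their past tense is set against the app group's future tense, app users enter by agreement, and no assignment step appears anywhere. If concurrent randomisation was intended, the Methods are wrong and need rewriting, so a correction is due on either reading. What stands is that the document does not show which side is the mistake. The finding is therefore that the Methods *as worded* exclude randomisation.

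**A matter for the SAP.** Covariate adjustment and details of the randomisation procedure can be left to other documents. Here, however, the protocol asserts a property that its own group definitions exclude, and an SAP cannot repair that.

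**Completion as timing, not selection.** The protocol does not expressly say that people who stopped home care early are left out. Its literal definition of the controls implies it, but what the control records contain is not described. The point on unequal selection is therefore supporting only.

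**The illustration rests on assumed biases.** This is correct. Any biased t-test would behave this way, and the false-positive table is not the error of most interest when equality is the hope. The masking calculation addresses that error, but with assumed inputs too. Neither is evidence about the bias in this study.

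**Conclusion.** The concern holds, with high confidence, and must be fixed. The label and the Methods cannot both be true. As described, the study is a non-randomised comparison of a prospective app cohort with previously treated controls, and its wording on efficacy is not supported.

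This conclusion rests only on the protocol's text and needs no calculation. The direction and size of any bias cannot be determined from the document. The illustrative figures depend on the assumed alpha, group sizes and biases. They show that modest bias matters, that it can hide a deficit as well as create a difference, and that enlarging the sample does not remove it.

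**What to change.** **1. Reconcile label and Methods, by one of two routes.**

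(a) *The Methods stand.* In the title, Study Design and Conclusion, describe the study as a non-randomised comparison of a prospective app cohort with previously treated controls. In the Background, drop the word *prospective* from the aside about the age cutoff (a minor edit, since the word is true of the app group).

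(b) *The label stands.* Rewrite the Methods so that concurrently enrolled patients are randomised to app or home care. This is a redesign.

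**2. Under (a), remove the efficacy claims.**

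- Objectives: state the aim as comparing ROM improvement between app users and previously treated home-care patients.
- Primary hypothesis: delete the closing clause about demonstrating efficacy.
- Conclusion: recast the whole sentence, since its wording on reducing costs and maintaining outcomes is also causal.
- Methods: the description of the Short MAC results as an effect of the intervention could be softened in the same pass.

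**3. Supporting, under (a): align the data-selection rules.** If control records include people who started but did not finish home care, include them, and keep all enrolled app participants in the main comparison. If they do not, show both the all-enrolled and the engaged-only app results and state that controls are completers. Apply the readmission data exclusion to both groups where records allow, or report the asymmetry as a limitation. Where records permit, taking consecutive controls who meet the inclusion criteria and adjusting for baseline factors held in both groups would help, but neither is needed to remove the contradiction.

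**Cost.** Items 1(a) and 2 are wording changes in six places, counting the title and Study Design separately, plus the optional Short MAC edit. Item 3 needs final ROM from app participants who would otherwise be excluded, and a check of what the control records hold. The price of 1(a) is a weaker claim, but a true one.

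### If past patients serve as controls, the protocol sets no period, source or rule for choosing the roughly 30 records, so record choice could shift the primary ROM comparison

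*Protocol*

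**What the plan says.** The control group is described twice in Methods. It is first defined by completion of care: "The control group are those who have completed traditional home health physical therapy following TKA". The source of the data is then given: "Data for the control group will be taken from approximately 30 individuals aged 45 to 64 that have previously completed traditional home health physical therapy". The providers are left open, with ROM improvement to be set against "a control group of patients who have completed traditional home care from a variety of physical therapists following TKA".

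The inclusion criteria are written for the study as a whole: "Inclusion criteria for the study consists of participants aged 45 to 64, the participant will have undergone unilateral TKA", followed by the condition of discharge from hospital straight to home. Only the exclusions that follow are confined to the app group.

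The app group is recruited forward in time as "approximately 30 participants who agree to use the smartphone app", with initial data taken within 48 hours of discharge. The primary objective is assessed "by comparing ROM improvement outcomes between the intervention group and the control", and the analysis is: "A two-tailed t-test for two independent groups will be used to compare the means for total ROM improvement". The primary hypothesis is that the two groups' outcomes are statistically equal.

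The Study Design section nevertheless describes a "Prospective randomized controlled trial comparing traditional home health care physical therapy to physical therapy provided via a smartphone app".

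**The concern.** When controls are past patients, choosing their records plays the part that enrolment plays in a prospective arm. It determines the control mean, so the rule for choosing has to be fixed before the outcomes are seen. Here the inclusion criteria say who may be a control, but nothing says which of those people will be. The protocol names no look-back period, no hospital, agency or referral source, and no consecutive, random or matched sampling.

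Two routes to bias stay open. First, whoever assembles the set might have ROM values at hand. Second, even a chooser who never sees ROM may draw records from a different period or a different surgical and rehabilitation practice than the app patients come from.

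Either would move the control mean, and the comparison as described has no matching or adjustment to absorb it. With a hypothesis of equal outcomes, both directions matter. A weak control set flatters the app and a strong one penalises it. A set that happens to fall near the app mean would support equality whatever the truth.

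**Working it through.** **Figure to reproduce.** None. The protocol gives about 30 per group but no alpha, power, ROM standard deviation, effect size or equivalence margin, and no count of eligible past records.

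**Inputs from the protocol.** About 30 controls, about 30 app participants, and a two-tailed two-sample t-test on ROM improvement.

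**Inputs assumed.** Normal outcomes in SD units, two-sided alpha of 0.05, 30 analysed per group, a pool of 60 or 90 eligible records, and a correlation r of 0 to 0.3 between being chosen and ROM improvement.

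**Step 1, precision.** The standard error of the difference is sqrt(2/30) = 0.258 SD.

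**Step 2, shift from partial selection.** Shift = r × i, where i = pdf(z)/p is the selection intensity when a fraction p of the pool is taken and z is the matching normal cut-point.

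| Pool | p | i | r = 0 | r = 0.2 | r = 0.3 |
|---|---|---|---|---|---|
| 60 | 0.50 | 0.80 | 0 | 0.16 SD | 0.24 SD |
| 90 | 0.33 | 1.09 | 0 | 0.22 SD | 0.33 SD |

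Relative to the standard error, the non-zero shifts run from 0.16/0.258 = 0.6 to 0.33/0.258 = 1.3 standard errors.

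**Step 3, effect on the test.** With no true difference and the control mean shifted by b SD, the noncentral t (58 df, noncentrality b × sqrt(30/2)) gives the chance of a significant result:

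| b (SD) | Chance of p < 0.05 |
|---|---|
| 0 | 5% |
| 0.2 | 12% |
| 0.25 | 16% |
| 0.3 | 21% |

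**Step 4, outer bound.** Suppose the 30 records with the lowest ROM improvement were always taken (20,000 simulated draws per pool size):

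| Eligible records | Shift in control mean | Chance of p < 0.05 |
|---|---|---|
| 33 | 0.17 SD | 12% |
| 40 | 0.41 SD | 44% |
| 60 | 0.79 SD | 94% |

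This is a ceiling for deliberate selection and nothing in the protocol suggests it would happen. It does show that the pool size, which the protocol does not give, governs how much could go wrong.

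These figures illustrate selection related to outcome. They do not measure differences in era or practice, for which the protocol offers no data.

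**The case against.** Several points on the other side are sound.

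- **Eligibility is not wide open.** A reader might infer that any past home health patient could be a control. The inclusion criteria are stated for the study, so the natural reading is that controls too need a unilateral TKA and discharge straight home. What stays open is the choice among people who meet those criteria.
- **Outcome-aware picking is not stated.** A reader might infer that records will be selected with the results in view. That ROM values exist follows reasonably from care being finished, but the protocol does not say who selects the records, what that person sees, or how control ROM was captured.
- **The bias need not be invisible.** The endpoint is improvement, so a starting ROM must exist, and comparing it between groups could expose some imbalances. It would not expose all of them.
- **The size is assumed.** Selection unrelated to ROM gives no shift from this route, and a pool barely above 30 leaves little to select. The range therefore has to start at zero.
- **The issue is conditional.** If the study is run as the randomized trial named under Study Design, controls are concurrent and the question falls away. If it is merely relabelled as non-randomized, the question remains.
- **Age reference date.** Whether age is taken at surgery or at data extraction affects only patients near the limits. It is worth a few words in the text and no more.

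An unseen SAP does not answer the core point. The source and sampling of controls are design matters that the protocol itself takes up, and an analysis applied after the records are chosen cannot undo the choice.

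**Conclusion.** The point holds, on condition that historical controls are kept. Within the inclusion criteria, the protocol leaves the period, the source and the choice of about 30 completed records unregulated, and it compares them without adjustment against a group enrolled forward in time. That is more than a missing detail, because the control mean depends on a choice for which no rule exists.

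The magnitude is illustrative: 0 to about 0.33 SD, or up to about 1.3 standard errors, resting on assumed pools of 60 to 90 records and correlations of 0 to 0.3. It should not be read as an estimate of bias in this trial. The protocol supports saying that there is room for biased selection. It does not support saying that such selection is planned or has occurred.

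**What to change.** First settle whether controls are randomized or historical. That decision is separate from this point. If they remain historical, replace the control-data sentence in Methods with a selection rule along these lines:

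- Controls are the most recent consecutive patients who meet the study inclusion criteria, with age taken at surgery, and who completed traditional home health physical therapy.
- They are counted back from the date app enrolment opens until about 30 with both a starting and a final ROM on record are reached.
- They come from the same referral sources as the app group where possible.
- The ordered list is fixed from discharge or referral dates before any ROM value is viewed. Records are then taken in that order, and the number skipped for missing ROM is reported.

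Counting back until the number is reached avoids a fixed window that might yield too few usable records, since the protocol gives no case volumes.

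The cost is protocol wording and the work of building a date-ordered list, with no added patients or visits. The sponsor loses the freedom to choose convenient records, will meet some incomplete ones, and may need a longer look-back, which weakens the match in era. The rule removes discretion over which records enter. It does not remove confounding from non-random allocation.
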